4.5.3. IRR events

Here, infusion related reactions will be analyzed through safety analysis set. IRR events can be divided into potential immediate, which refers to IRRs occurring within 24 hours of donanemab administration, and potential non-immediate, which refers to IRRs occurring after 24 hours of donanemab administration. A Fisher's exact test will be employed to infer if potential immediate or potential non-immediate IRR incidence proportion is identical or not between one alternative treatment arm and the standard treatment arm. Whether the severity of immediate or non-immediate IRR events (severe vs. non-severe) is the same or not between one alternative dosing regimen and the standard dosing regimen will be confirmed through a Fisher's exact test as well.

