#### 4.1.1. Treatment Arms and Titration Regimen Outline

All participants will receive a dosing regimen that includes donanemab, but at different dose levels and frequency of dosing. Placebo is given at specific visits to preserve the blind for the different dosing regimens.

This table describes the planned dosing regimens for the first 16 weeks. After Week 16, all participants are targeted to receive 1400 mg monthly of donanemab until they meet the dose stopping criteria or until the end of the study.

Visit Number	2	3	4	5	6	7	8	9	10
Study Week	0	2	4	6	8	10	12	14	16
Treatment Arm					Dose (mg)	)			
1 standard regimen	700	PBO	700	PBO	700	PBO	1400	PBO	1400
2	700	PBO	PBO	PBO	1400	PBO	1400	PBO	1400
3	350	PBO	700	PBO	1050	PBO	1400	PBO	1400
4	350	350	350	350	350	350	700	700	1400

Abbreviations: PBO = placebo.

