# 6. Study Intervention(s) and Concomitant Therapy

Study intervention is defined as any investigational intervention(s), marketed product(s), placebo, or medical device(s) intended to be administered to or used by a study participant according to the study protocol.

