# 9.3.5. Safety Analyses

An overview of AEs, including the number and percentage of participants who died, experienced SAEs, and discontinuations from study treatment due to an AE and TEAE, will be provided for all 4 dosing regimens. TEAE in the Safety Analysis Set will be defined as events that first occurred or worsened on or after the day of first infusion.

Laboratory measurements will be analyzed using continuous data (change from baseline) and categorical or ordinal data (proportion of treatment-emergent abnormalities). If there are multiple records of laboratory measurements at baseline or postbaseline visit, the last record will be used.

Vital sign measurements and weight will be analyzed using continuous data (change from baseline) and categorical data (proportion of potentially clinically significant changes). Vital sign measurements include systolic and diastolic blood pressure and pulse, orthostatic diastolic and orthostatic systolic blood pressures and orthostatic pulse, and temperature.

Hypersensitivity and IRR will be analyzed by:

- **Potential immediate** defined as TEAEs occurring on the date of infusions, or for which a hypersensitivity follow-up form indicates the event occurred within 24 hours of study intervention administration, and
- **Potential non-immediate** defined as TEAEs that are not immediate but occur prior to the administration of a subsequent infusion.

The number and percentage of participants who experienced a TEAE of hypersensitivity or IRR will be reported across the 4 treatment groups.

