4.6.7. Hypersensitivity/Infusion Related Reactions

Section 4.5.3 described ways to explore whether alternative dosing regimen will impact IRR frequency and severity. In this subsection, both hypersensitivity and IRRs will be analyzed and summarized from safety analysis set. Hypersensitivity and IRRs will be broken out between potential immediate (defined as TEAEs occurring on the date of infusions, or for which a hypersensitivity follow-up form indicates the event occurred within 24 hours of study drug administration) and potential non-immediate (defined as TEAEs that are not immediate but occur prior to the administration of a subsequent infusion).

The AE database will be searched using predefined SMQs to identify preferred terms (PTs) that map hypersensitivity events or IRRs in both potential immediate and potential non-immediate analysis periods. For each treatment arm, the number and percentage of patients who experienced a TEAE of hypersensitivity or IRR will be reported.

The following summary tables may be provided about hypersensitivity/IRRS:

- treatment-emergent serious hypersensitivity, anaphylactic and IRRs
- potential immediate hypersensitivity, anaphylactic and IRRs by maximum severity
- potential non-immediate hypersensitivity, anaphylactic and IRRs by maximum severity
- symptoms for potential immediate hypersensitivity, anaphylactic and IRRs
- symptoms for potential non-immediate hypersensitivity, anaphylactic and IRRs.

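### SAP 4.5.3 times infusion reactions from donanemab with an open-ended late category; SAP 4.6.7 and Protocol 9.3.5 time them from any study infusion, yet the Fisher tests use the 4.5.3 split

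*SAP*

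**What the plan says.** SAP 4.5.3 serves the tertiary objective on IRR frequency and severity. It defines the first group as "potential immediate, which refers to IRRs occurring within 24 hours of donanemab administration". Its definition of the second group reads "potential non-immediate, which refers to IRRs occurring after 24 hours of donanemab administration". It then plans Fisher's exact tests of each alternative arm against standard on these two groups, for incidence and for severe versus non-severe events. SAP 4.1 sets the level at two-sided 0.05.

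SAP 4.6.7 uses the same labels for hypersensitivity and IRRs. Immediate events are "defined as TEAEs occurring on the date of infusions, or for which a hypersensitivity follow-up form indicates the event occurred within 24 hours"; here the clock runs from study drug. Non-immediate events are "defined as TEAEs that are not immediate but occur prior to the administration of a subsequent infusion". This section plans counts, percentages and summary tables by arm and names no test. It refers back to 4.5.3 but does not reconcile the two rules.

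Protocol 9.3.5 agrees with SAP 4.6.7: immediate events are "defined as TEAEs occurring on the date of infusions", or those for which the follow-up form "indicates the event occurred within 24 hours of study intervention administration". Protocol Section 6 makes clear that study intervention includes placebo: "Study intervention is defined as any investigational intervention(s), marketed product(s), placebo, or medical device(s) intended to be administered". Protocol 4.1.1 explains why the arms differ in placebo use: "Placebo is given at specific visits to preserve the blind for the different dosing regimens".

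**The concern.** One report would carry two meanings of the same labels, and the version that departs from the protocol is the one tested between arms. The arms receive different numbers of placebo infusions in the first 16 weeks. A clock that starts only at donanemab can therefore put the same infusion-day reaction in different groups depending on the arm. If the sentence is programmed as written, Arm 4 would tend to look worse than standard on immediate reactions and better on non-immediate ones, partly because of the definition. For Arm 2 the tilt runs the other way, and it comes from a single visit.

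**Working it through.** The documents state no power or sample-size figure that depends on the IRR split, so there is none to reproduce. The check sets the definitions side by side, counts infusions, and then illustrates the size.

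**1. Definitions**

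| | SAP 4.5.3 | SAP 4.6.7 and Protocol 9.3.5 |
|---|---|---|
| Clock starts at | donanemab | any study infusion |
| Immediate | up to 24 hours | calendar day of infusion, or form shows 24 hours or less |
| Non-immediate | after 24 hours, no end | not immediate, and before the next infusion |
| Used for | Fisher tests | descriptive tables |

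**2. Infusions at Visits 2 to 10** (dose table, Protocol 4.1.1 and SAP 1.2)

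Reading check, mg before Week 16:
- Arm 1: 700 + 700 + 700 + 1400 = 3500
- Arm 2: 700 + 1400 + 1400 = 3500
- Arm 3: 350 + 700 + 1050 + 1400 = 3500
- Arm 4: 6 × 350 + 2 × 700 = 3500

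This agrees with the total stated in SAP 1.2.

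| Arm | Donanemab | Placebo | Placebo visits |
|---|---|---|---|
| 1 | 5 | 4 | 3, 5, 7, 9 |
| 2 | 4 | 5 | 3, 4, 5, 7, 9 |
| 3 | 5 | 4 | 3, 5, 7, 9 |
| 4 | 9 | 0 | none |

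The schedule of activities requires more than 7 days between infusions at Visits 2 to 10. A reaction on a placebo day is therefore always more than 24 hours after the last donanemab dose.

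**3. Filing under the literal 4.5.3 rule, against Arm 1**
- Arm 4: differs at Visits 3, 5, 7 and 9 (non-immediate in Arm 1, immediate in Arm 4).
- Arm 2: differs at Visit 4 only (immediate in Arm 1, non-immediate in Arm 2).
- Arm 3: no visit differs.
- From Visit 10 all arms are planned to receive donanemab, so nothing further differs.

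**4. Illustration for Arm 4 versus Arm 1**

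Assumptions: 200 participants per arm (800 / 4), full attendance, Visits 2 to 10 only, the same chance r of an infusion-day reaction at every infusion in every arm, and no other non-immediate reactions. The documents do not give r, so a range is shown.

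Expected participants with at least one event = 200 × (1 − (1 − r)^k), where k is the number of infusions of the relevant kind. At r = 0.5%:
- Arm 1 immediate: 200 × (1 − 0.995^5) = 5.0
- Arm 4 immediate: 200 × (1 − 0.995^9) = 8.8
- Arm 1 non-immediate from placebo days: 200 × (1 − 0.995^4) = 4.0
- Arm 4 non-immediate from placebo days: 0

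The chance of a significant result is the sum of the two binomial probabilities multiplied together, over all pairs of counts with a two-sided Fisher p of at most 0.05.

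| r | Immediate, Arm 1 vs 4 | Non-immediate, Arm 1 vs 4 | Significant, immediate | Significant, non-immediate | Significant, immediate, any-infusion rule |
|---|---|---|---|---|---|
| 0.2% | 2.0 vs 3.6 | 1.6 vs 0 | 3.0% | 0.6% | 1.5% |
| 0.5% | 5.0 vs 8.8 | 4.0 vs 0 | 11.5% | 20.9% | 2.7% |
| 1% | 9.8 vs 17.3 | 7.9 vs 0 | 25.3% | 80.3% | 3.3% |
| 2% | 19.2 vs 33.3 | 15.5 vs 0 | 49.4% | 99.9% | 3.6% |

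Under the any-infusion rule all nine infusions count in every arm, so expected immediate cases are equal (8.8 each at r = 0.5%).

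The non-immediate column depends only on the placebo-day rate, because Arm 4 has no placebo days. The immediate column also needs equal rates on placebo and donanemab days. If the placebo-day rate were zero, both rules would file infusion-day reactions alike. A 0.5% donanemab-day rate would then still give 5.0 versus 8.8 under either rule, as a genuine effect of 5 versus 9 donanemab infusions.

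**The case against.** The strongest reply is that donanemab in 4.5.3 simply means study drug. SAP 6.2 calls the infusions at all visits donanemab infusions, although Arms 1 to 3 receive placebo at some of them. The safety set is defined by exposure to donanemab in SAP Section 3 and by exposure to treatment in SAP 4.1. Sites are blinded and cannot time a reaction from donanemab alone, and the follow-up form counts from study drug. On that reading the arm-dependent filing vanishes. This stands as a real possibility, but the text does not settle it: SAP 1.2 separates donanemab from placebo, SAP 4.6.7 says study drug, and an analyst could apply 4.5.3 literally after unblinding.

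Even on the loose reading, two differences remain. A reaction on the day after an infusion but within 24 hours is immediate under 4.5.3, whereas under 4.6.7 it needs the form to show it. The open end has little effect while dosing continues, because an infusion is planned at every visit from 2 to 24, but it matters after a participant's last infusion.

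Two further replies also stand. The two sections cover different event sets (IRRs only, against hypersensitivity and IRRs), so their counts would differ in any case. And the size shown above rests on assumed rates, while Protocol 2.3.1 associates these reactions with donanemab infusion, which suggests that placebo-day rates may be low.

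A reader might infer that all three comparisons are biased, because Arms 1 to 3 all have placebo days and Arm 4 has none. The documents do not support that: each test is against Arm 1, which shares its placebo visits with Arm 3 and differs from Arm 2 at one visit. Nor do they support reading any excess of immediate reactions in Arm 4 as an artefact, given its nine donanemab infusions against five.

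**Conclusion.** The conflict between SAP 4.5.3 and both SAP 4.6.7 and Protocol 9.3.5 is plain on the text, and the planned tests use the version that departs from the protocol. Arm-dependent filing follows only if 4.5.3 is applied literally. It then touches Arm 4 versus standard at four visits and Arm 2 versus standard at one. Its size depends on a placebo-day reaction rate that the documents do not give: negligible near 0.2%, and enough to produce spurious significance at 0.5% to 1% under the stated assumptions. The objective is tertiary, no multiplicity adjustment is planned, and the primary analysis and sample size are untouched. This is a minor point, worth correcting because a literal program would distort a planned comparison.

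**What to change.** In SAP 4.5.3, replace both definitions with those of SAP 4.6.7 and Protocol 9.3.5, counted from any study infusion, donanemab or placebo, and use them for the Fisher tests of incidence and severity.

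The borrowed rule has gaps of its own, so also state how to classify:
- events after a participant's last infusion, where there is no next infusion to close the window (this includes participants who stop at Visit 12 or 19 on the plaque criteria and stay in the study);
- events on the infusion day that start before the infusion;
- events with no clock time and no follow-up form.

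The cost is one or two SAP sentences. The data are already needed for 4.6.7, and the tests themselves do not change.

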# 3. Objectives, Endpoints, and Estimands

Objectives	Endpoints
Primary	
To assess the effect of alternative donanemab dosing regimens versus the standard donanemab dosing regimen on ARIA-E frequency	Proportion of participants with any occurrence of ARIA-E by Week 24
Secondary	
To assess the effect of alternative donanemab dosing regimens versus standard donanemab dosing regimen on ARIA-E frequency	Proportion of participants with any occurrence of ARIA-E by Week 52
To assess the effect of alternative donanemab dosing regimens versus standard donanemab dosing regimen on brain amyloid deposition	Change from baseline in brain amyloid plaque deposition as measured by amyloid PET scan through  Week 24  Week 52  Week 76
To evaluate the effect of alternative donanemab dosing regimens on ARIA events	
 
Proportion of participants with any occurrence of ARIA-H by
 
Week 24
 
Week 52
 
ARIA-E and ARIA-H by severity
 

To assess peripheral PK and presence of anti-donanemab antibodies	
 
Serum PK of donanemab
 
ADAs against donanemab, including TE-ADAs and neutralizing antibodies
 

Tertiary/Exploratory	
To explore characteristics that predict risk of ARIA-E and ARIA-H	
 
Association between exploratory MRI imaging sequences and the occurrence and severity of ARIA events
 
Association between blood-based biomarkers and the frequency and severity of ARIA events         
 
NfL
 
pTau
 
Aß levels (40 and 42)
 
 
 

Objectives	Endpoints
	

 GFAP

 sTREM2, and

 hsCRP.

To evaluate the effect of alternative donanemab dosing regimens on IRR	IRR events frequency and severity

Abbreviations: Aß = amyloid-beta peptide; ADA = antidrug antibody; ARIA = amyloid-related imaging abnormalities; hsCRP = high-sensitivity C-reactive protein; GFAP = glial fibrillary acidic protein; IRR = infusion-related reactions; NfL = neurofilament light chain; PK = pharmacokinetic; pTau = phosphorylated tau; sTREM2 = soluble triggering receptor expressed on myeloid cells 2.

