### **Assessment of intensity**

The investigator will make an assessment of intensity for each AE and SAE reported during the study and assign it to 1 of the following categories:

- Mild: A type of adverse event that is usually transient and may require only minimal treatment or therapeutic intervention. The event does not generally interfere with usual activities of daily living.
- Moderate: A type of adverse event that is usually alleviated with additional specific therapeutic intervention. The event interferes with usual activities of daily living, causing discomfort but poses no significant or permanent risk of harm to the research participant.
- Severe: A type of adverse event that interrupts usual activities of daily living, or significantly affects clinical status, or may require intensive therapeutic intervention. An AE that is assessed as severe should not be confused with an SAE. Severe is a category utilized for rating the intensity of an event; and both AEs and SAEs can be assessed as severe.

An event is defined as "serious" when it meets at least 1 of the predefined outcomes as described in the definition of an SAE, NOT when it is rated as severe.

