4.6.2.	Adverse events	
4.6.3.	Clinical laboratory evaluation	23
4.6.4.	Vital signs and other physical findings	24
4.6.5.	Columbia-Suicide Severity Rating Scale	25
4.6.6.	Amyloid-Related Imaging Abnormalities (ARIA)	26
4.6.7.	Hypersensitivity/Infusion Related Reactions	27
4.6.8.	Safety MRIs	27
4.7.	Interim Analysis	28
5.	Sample Size Determination	29
6.	Supporting Documentation	30
6.1.	Appendix 1: Demographic and Baseline Characteristics	
6.2.	Appendix 2: Treatment Compliance	30

LY3002813

7.	References	32
6.5.	Appendix 5: Handling Missing Data from Participant Dropouts	31
6.4.	Appendix 4: Multicenter Studies	31
6.3.	Appendix 3: Concomitant Therapy	30

Version history

This SAP for Study I5T-MC-AACQ is based on the protocol dated 28OCT2022.

SAP Version	Approval Date	Change	Rationale
1.0	27APR2023	Not Applicable	Original version
2.0		• Change reduction in proportion to difference in proportion in Section 1.1.	• Such a change is more aligned with the language in primary objective.
2.0		• In Section 2, define p_1 - p_4 .	Needs such definitions.
2.0		• Introduce relative risk in addition to relative risk reduction.	• Highlight the fact a relative risk <1 implies a positive relative risk reduction.
2.0		• Add posterior probability being more than 0.8 to be considered as a significant result.	• SAP (V1.0) did not mention benchmark value of posterior probability to be considered significant.
2.0		Replace amyloid PET analysis set with evaluable efficacy analysis set.	• Current EES includes any randomized patient with baseline and at least 1 post-baseline measure of interest.
2.0		Add per-protocol analysis set.	• SAP (V1.0) did not include this analysis set.
2.0		• For the Bayesian model specification, baseline PET values are divided into tertiles.	• In previous SAP, baseline PET in centiloids was a continuous covariate in the logistic regression model
2.0		• Change threshold value to 0.8.	• SAP (V1.0) did not cite this number correctly.
2.0		• Analysis of PET data at 24, 52, and 76 weeks.	• SAP (V1.0) used around 24, 52, and 74 weeks.
2.0		Minor editing.	• Increase readability.

2.0	Add PET analysis based on per-protocol analysis set.	• This is a sensitivity analysis for PET results using randomized population.
2.0	Add an alternative method of CMH test to analyze severity of ARIA- E and ARIA-H.	• Previously, only Fisher's exact test was proposed. CMH test can treat severity as an ordinal measurement.

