4.1. General Considerations

As 4 donanemab dosing regimens including the standard one are available for Study AACQ, any safety or biomarker analysis will involve 3 comparisons: 1) dose skipping vs. standard dosing; 2) titration vs. standard dosing; 3) Cmax (concentration maximum) vs. standard dosing.

Safety analyses will include subjects who are randomized to study treatment and who take at least 1 dose of treatment. Subjects will be analyzed according to the treatment arm to which they were assigned.

Unless otherwise specified, analyses for ARIA events are based on MRI findings or AE (adverse events) reporting. ARIA safety analyses will cover both ARIA-E and ARIA-H events by Week 24 as well as by Week 52. Bayesian logistic regression method is proposed to obtain a posterior distribution regarding relative risk reduction in ARIA-E or ARIA-H at Week 24 or 52 for each of 3 comparisons mentioned above. The details of logistic regression model, prior elicitation, and computation for the posterior distribution will be presented in Section 4.3.2. From each derived posterior distribution of RD_{21} , RD_{31} , and RD_{41} , summary statistics will be reported which include posterior mean, posterior median, posterior mode, a 2-sided equal-tailed 95% posterior interval (often cited as credible interval in Bayesian literature), and a posterior probability of achieving a minimum of 20% relative risk reduction in ARIA-E.

Frequentist methods will be used for the rest of the study objectives. All frequentist tests will be conducted at a 2-sided alpha level of 0.05; 2-sided confidence intervals (CIs) will be displayed with a 95% confidence level.

Unless otherwise noted baseline is defined as the last measurement prior to dosing. When change from baseline is assessed, subjects will only contribute to the analysis if both a baseline and a post-baseline measurement are available. Endpoint is the last non-missing post-baseline measurement within the time period for the given analysis.

To allow for evaluation of the primary and secondary hypotheses at 24 and 52 weeks, database locks and the assessments of corresponding primary and secondary objectives are expected to occur after all participants in the Safety Analysis Set have had the opportunity to complete visits 12 and 19 including PET and MRI assessments. The sponsor may choose not to have a separate database lock after visit 19 and wait to perform the analyses for 52-week data until the final database lock.

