4.4.3. ARIA-H incidence and severity of ARIA events

ARIA-H includes microhemorrhage and superficial siderosis. Total number of participants with microhemorrhage, superficial siderosis, as well as overall ARIA-H events will be reported at Week 24 and Week 52 by treatment arm. Incidence proportion of microhemorrhage, superficial siderosis, and overall ARIA-H per arm will be estimated from both time points. A posterior distribution of relative risk reduction in ARIA-H between one alternative dosing regimen and the standard dosing regimen by Week 24 or by Week 52 will be derived through a Bayesian logistic regression using 24-week or 52-week ARIA-H data coupled with priors constructed in a similar way as mentioned in Section 4.3.2 or Section 4.4.1. Then a posterior probability of at least 20% relative risk reduction in ARIA-H in 24 weeks or 52 weeks comparing one alternative treatment

arm versus the standard arm will be calculated. Sensitivity analyses will be similar to approaches as mentioned in Section 4.3.3.

For outputs including radiographic severity, below table contains the definitions used for 3-point ARIA-E and ARIA-H categorizations. A 5-point ARIA-E categorization has mild+ and moderate+ levels besides mild, moderate, and severe levels defined by the 3-point ARIA-E categorizations. Among participants with at least 1 ARIA-E or ARIA-H event during the study, number and percentage of participants with their maximum radiographic severity value in the categories of mild, moderate, and severe will be presented by treatment arm from 24-week and 52-week ARIA data when a 3-point rating of ARIA severity is used. Among participants with at least 1 ARIA-E event during the study, number and percentage of participants with their maximum radiographic severity value using the 5-point severity scale will be reported by treatment arm for both times points as well. At Week 24 and Week 52, Fisher's exact tests will be applied to determine if severe ARIA-E or ARIA-H events are distributed evenly while comparing the dosing skip regimen vs. standard dosing regimen, the titration regimen vs. standard dosing regimen.

An additional approach to Fisher's exact test will be used to investigate the association between treatment arm and ARIA (-E or -H) severity with a Cochran-Mantel-Haenszel (CMH) test. Fisher's exact test treats severity as a nominal variable whereas CMH can handle severity as an ordinal variable.

Table 4.1. Radiographic severity of ARIA-E and ARIA-H.

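### SAP 4.5.3 tests the severity of infusion-related reactions only as severe vs non-severe, so a shift between mild and moderate cannot be detected by that test; an ordinal test among reactors should be added beside it

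*SAP*

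**What the plan says.** Protocol section 3 and SAP 1.1 list the endpoint among the tertiary/exploratory ones as "IRR events frequency and severity". Neither document attaches a rate, sample size or power to it.

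Protocol 10.3.4 provides three ordered grades (mild, moderate, severe): "The investigator will make an assessment of intensity for each AE and SAE reported during the study and assign it to 1 of the following" grades.

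SAP 4.5.3 plans two kinds of Fisher test, each comparing an alternative regimen with the standard one, separately for potential immediate and potential non-immediate reactions. For frequency: "A Fisher's exact test will be employed to infer if potential immediate or potential non-immediate IRR incidence proportion is identical or not". For severity: "Whether the severity of immediate or non-immediate IRR events (severe vs. non-severe) is the same or not between one alternative dosing regimen" and the standard regimen. The section does not say whether the severity comparison counts all treated participants, participants with an IRR, or events. SAP 4.1 sets the level: "All frequentist tests will be conducted at a 2-sided alpha level of 0.05".

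Severity of IRRs appears in two other places, both descriptive. SAP 4.6.2 commits to summaries of treatment-emergent adverse events with maximum severity, by preferred term and arm. SAP 4.6.7 lists tables by maximum severity for immediate and non-immediate hypersensitivity, anaphylactic and infusion-related reactions, but only as optional output.

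For ARIA severity the SAP goes further. Section 4.4.3 adds a CMH test to the Fisher test and gives the reason: "Fisher's exact test treats severity as a nominal variable whereas CMH can handle severity as an ordinal variable". The version history for SAP 2.0 repeats it: "CMH test can treat severity as an ordinal measurement". Section 4.5.3 has no counterpart.

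**The concern.** IRR severity is recorded on an ordered three-grade scale, and the analysis discards one of its two boundaries before testing. The discarded boundary has meaning in the protocol's own definitions: a moderate event interferes with usual daily activities, and a mild one generally does not. The arms differ in the dose given at the early infusions (350 to 1400 mg in the first 16 weeks), so whether reactions are graded differently by regimen is a fair question for this trial.

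At stake is the severity half of an exploratory endpoint. A regimen that turned many mild reactions into moderate ones would give a non-significant result in the only IRR severity test planned, and a report could read that as no difference in severity. The SAP has already accepted the argument for an ordinal test for ARIA, so the omission is also an internal inconsistency.

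**Working it through.** There is no IRR figure in the documents to reproduce.

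**Inputs.** From the documents: about 800 participants randomised 1:1:1:1, so 800/4 = 200 per arm; two-sided alpha 0.05; three grades. Assumed, because the documents are silent: IRR incidence 5, 10, 15 or 20% per arm, which is 10, 20, 30 or 40 expected cases among 200; and the grade mixes below.

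**Step 1: what the planned test can see.** Its null hypothesis is that the severe share is equal in the two arms. Take mild/moderate/severe 65/30/5 in one arm and 35/60/5 in the other. Thirty points of reactions have moved from mild to moderate, and the severe share is 5% in both. The null hypothesis is true, so the test can reject only by chance. This step needs no rate.

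**Step 2: how many severe cases Fisher needs.** With all k severe cases in one of two arms of 200, the two-sided p-value is 2 × C(200,k)/C(400,k).
- k = 5: 2 × (200·199·198·197·196)/(400·399·398·397·396) = 0.061
- k = 6: multiply by 195/395, giving 0.030

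The smallest significant splits are 6 vs 0, 8 vs 1 and 10 vs 2, and they are the same at 180 per arm.

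**Step 3: the ordinal test on one data set.** Score mild = 1, moderate = 2, severe = 3 among participants with an IRR. The row-mean-score statistic is Q = (N − 1) × SSB/SST on 1 degree of freedom, where SSB and SST are the between-arm and total sums of squares of the scores. Take 20% incidence and exactly the mixes of step 1: 26/12/2 vs 14/24/2.
- Mean scores: 56/40 = 1.40 and 68/40 = 1.70; overall 1.55
- SSB = 2 × 40 × 0.15² = 1.8
- SST = (40×1 + 36×4 + 4×9) − 80 × 1.55² = 220 − 192.2 = 27.8
- Q = 79 × 1.8/27.8 = 5.12, p = 0.024
- Fisher on 2/40 vs 2/40: p = 1

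**Step 4: power for the step 1 shift, equal incidence in both arms.** Simulated at 200 per arm; the small ranges reflect separate simulation runs and whether the number of cases is fixed or random.

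| Assumed incidence | Fisher, severe vs not | CMH among reactors | CMH on all treated, none=0 to severe=3 |
|---|---|---|---|
| 5% | ≤1.3% | 20-23% | 7% |
| 10% | ≤1.3% | 37-38% | 8-9% |
| 15% | ≤1.3% | 50-51% | 11-12% |
| 20% | ≤1.3% | 63% | 14% |

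With no difference between arms, the CMH test among reactors rejects in 4-5% of simulations.

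**Step 5: which denominator.** If incidence is halved and the grade mix is unchanged, the all-treated score rejects in about 23-74% of trials over the same incidence range. It mainly repeats the frequency test that 4.5.3 already contains.

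**The case against.** The strongest reply is that the endpoint is exploratory, carries no power claim and is not adjusted for multiplicity. Severe reactions are the ones that may need intensive treatment, so severe vs non-severe is a defensible safety contrast. This stands. It is a reason to keep the Fisher test and to rank the point as minor, but not a reason to leave the other boundary untested.

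A reader might infer four stronger things that the documents do not support.
- **That the test has almost no power.** No IRR rate or severe share is given. At an assumed 20% incidence with 20% of cases severe, Fisher on 200 per arm has 32% power for a doubling of severe cases and 81% for a tripling. With a severe share of 10% or less it has at most 13% and 44%.
- **That a mild-to-moderate shift would go unseen.** The maximum-severity summaries committed in SAP 4.6.2 would show it by preferred term, though not split into immediate and non-immediate reactions. The 4.6.7 tables would show that split if they are produced.
- **That collapsing the grades is the only limit.** Few reactions also limit power; the ordinal test stays below 80% in every mild-to-moderate scenario in the table.
- **That Fisher should give way to an ordinal score over all treated participants.** Such a score has only 7-14% power for the shift in question and responds mainly to incidence. It is not what 4.4.3 does either: there severity is tabulated among participants with an event, and CMH is an addition to Fisher.

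**Conclusion.** The point holds in a limited form. As written, the only test of IRR severity cannot detect a shift between mild and moderate, whatever its size; this follows from the wording of SAP 4.5.3 and needs no assumption. Weak power against a change in severe reactions is conditional on those reactions being uncommon. The 6 vs 0 threshold is exact; the rates are unknown.

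The gain from an ordinal test among reactors, from about 1% at most to about 20-63% in the shift examined, rests on assumed incidences of 5-20% and an assumed 5% severe share. It is a clear improvement but does not make the comparison well powered. Nothing here touches the primary or secondary analyses.

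**What to change.** In SAP 4.5.3:
- Keep the severe vs non-severe Fisher test and state its denominator.
- Add a CMH row-mean-score test of each participant's maximum IRR severity (mild = 1, moderate = 2, severe = 3) among participants with at least one IRR. Compare each alternative regimen with the standard one, separately for immediate and non-immediate reactions.
- Show the mild/moderate/severe distribution by arm beside the test, and read it together with the planned incidence test.
- Make the maximum-severity tables in 4.6.7 firm rather than optional.
- Do not substitute an all-treated 0-3 score.

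The cost is a few sentences and a small programming addition. The grades are already collected, and the SAP already uses a CMH test for ARIA severity. Three comparisons times two timing classes gives six more unadjusted p-values, to be labelled exploratory. There are two other small drawbacks. The scores assume equal spacing between grades. The test also conditions on having had a reaction, so it describes severity among reactors and is not a randomised comparison.
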